## 1.0 Objectives / Specific Aims

- This is a prospective, single-arm, pre-post cohort study to look at the efficacy of the ZIDA Control Sock as an add-on therapy for patients with overactive bladder (OAB) and urgency urinary incontinence (UUI) who are already on preexisting stable OAB pharmacotherapy. The ZIDA sock is a new device, engineered as a wearable neuromodulation system in a sock, that provides transcutaneous tibial nerve stimulation to help relieve symptoms of OAB such as urinary urgency, urinary frequency, and urgency urinary incontinence. The device is non-invasive and has been well-tolerated overall in previous studies. A small number of studies have been conducted on this new device as primary therapy for OAB. We aim to study the effects of adding ZIDA onto the treatment plan of patients who are already on stable pharmacotherapy OAB with persistent symptoms.
- **Primary Objective:** To evaluate the mean change in total daily UUI episodes after addition of ZIDA therapy to patients on stable pharmacotherapy with OAB and persistent UUI. We will evaluate the mean change in episodes from baseline to weeks 1, 4, and 8 for interim analysis, and to week 12 for final analysis. Interim analyses will be descriptive and will not be used for stopping the study early or hypothesis testing.
- **Secondary Objectives:** (1) To assess change in daily urgency episodes (2) to assess change in daily urinary frequency; (3) To assess changes in patient-reported outcomes including a disease specific outcomes questionnaire (OAB-q Short Form (OAB-q SF) total score) (4) to assess a patient's impression of improvement (Patient Global Impression of Improvement (PGI-I)); (5) To assess usability, satisfaction, and adherence (with Device Use Log and Usability and Satisfaction Survey); and (6) To describe any device-related adverse events (with Adverse Event Log).
- We hypothesize that adding ZIDA therapy to the treatment regimen of OAB-wet patients already on stable pharmacotherapy will reduce their total daily urgency urinary incontinence episodes over 12 weeks.

## 2.0 Background

Overactive bladder (OAB) is a chronic condition characterized by urinary urgency, either with or without urgency urinary incontinence (UUI). Those with UUI are classified as OAB-wet, and those without UUI are classified as OAB-dry. OAB patients also typically have increased daytime frequency and nocturia, which is not accounted for by another pathology. It is estimated that between 12-16% of the population has OAB, and this condition has significant negative impacts on patient's quality of life. The conservative treatment options for OAB are lifestyle changes, pelvic floor muscle training, and pharmacotherapy. The more invasive and expensive treatment choices include intravesical botulinum toxin injections and sacral neuromodulation. Unfortunately, many OAB patients struggle to follow the lifestyle changes, while many others remain symptomatic despite pharmacotherapy. Some also discontinue their drug therapy due to cost or side effects such as dry mouth, constipation, and cognitive concerns.

Neuromodulation for OAB is thought to work by stimulating afferent nerves to the sacral spinal cord, which suppresses abnormal afferent bladder signaling and promotes guarding reflexes. This stimulation also regulates other central nervous system pathways, such as the prefrontal cortex and limbic system, which play a role in urgency perception and bladder control. Neuromodulation can be delivered in several ways; percutaneously, transcutaneously, or more centrally, just depending on the clinical setting. Percutaneous tibial nerve stimulation (PTNS)

and transcutaneous tibial nerve stimulation (TTNS) both deliver electrical stimulation adjacent to the medial malleolus in the lower extremity. They target the tibial nerve and primarily stimulate the S2 to S3 pathways, as well as the L4 and L5 pathways. Multiple studies have shown benefit between the different delivery methods. Systematic reviews have shown that both PTNS and TTNS improve OAB symptoms, including urgency, frequency, and incontinence episodes.

Recent studies have shown that TTNS can be used effectively and safely outside of the clinic. Wearable at-home TTNS devices offer comparable symptom improvement while reducing treatment burden for patients. The ZIDA Control Sock is an FDA-cleared TTNS device that can be self-administered at home. A recent study conducted on another wearable TTNS device found that it is safe, effective, and feasible for patients to use neuromodulation devices for at-home treatment sessions. Prior randomized controlled trials conducted on the ZIDA sock have found statistically significant improvements in total daily incontinence episodes and OAB-related quality of life.

Despite first and second line therapy such as pharmacotherapy, many patients with OAB continue to have urinary urgency incontinence episodes. Current pharmacotherapy for OAB includes agents which either antagonize muscarinic receptors or stimulate beta-3 receptors in the lower urinary tract. These agents are not completely effective and have dose-limiting adverse effects. Currently, it is unclear whether TTNS, which has a different mechanism of action as compared to medications, can be used as an add-on therapy in these OAB patients on pharmacotherapy to provide even more symptom relief. TTNS is non-invasive and studies show that it does not have significant adverse events. This study aims to evaluate whether the addition of the ZIDA device in patients with an incomplete response to pharmacotherapy will provide further relief of symptoms and improve quality of life.

### 3.0 Intervention to be studied

- The ZIDA device is a wearable, non-invasive sock, used for OAB treatment. This study will evaluate its use as an adjunct (add-on) therapy to standard pharmacologic treatment, which has not previously been studied. While studies have shown the efficacy of ZIDA as a stand-alone home therapy for OAB, it has not yet been evaluated in combination with ongoing OAB pharmacotherapy. This study will help us better understand whether adding TTNS to a patient's medication regimen is practical, safe, and helpful for symptom control.
- The ZIDA device has reported minimal adverse events. During prior studies it was found that two patients had mild cases of foot pain and two other patients had unrelated urinary tract infections. These events were minimal and self-resolved quickly without discontinuing treatment.
- The treatment sessions will be the participant wearing the ZIDA Control Sock (with conductive gel), attaching the small control unit device, and turning this on to administer electrical stimulation for 30 minutes. The stimulation is set to a comfortable level that may produce a mild tingling sensation or mild toe movement; this indicates the activation of the tibial nerve.
- The intervention will be once weekly 30-minute sessions using the ZIDA sock for 12 consecutive weeks. Each patient will serve as their own control.

## 4.0 Study Endpoints

- Our primary endpoint is to evaluate the mean change in total daily UUI episodes from baseline to week 12. Exploratory interim analyses at weeks 1, 4, and 8 will be descriptive. Our secondary endpoints include urgency episodes, total voiding frequency per day, QOL questionnaire Overactive Bladder Questionnaire (1-Week Recall) (OAB-Q SF 1W), Patient Global Impression of Improvement (PGI-I) responder, and any adverse events.
- Device usability and satisfaction will be measured at Week 12 using the Usability & Satisfaction Survey. This survey is a six-item questionnaire adapted from prior OAB studies. Five items are rated on a five-point Likert scale (1 = Strongly disagree to 5 = Strongly agree) to measure device ease of use, comfort, clearness of instructions, convenience, and patient willingness to continue therapy. There is also an open-ended feedback question. We'll summarize responses to get a sense of usability and patient experience.
- Adherence will be measured as the proportion of prescribed weekly sessions completed, based on the participant's Device Use Log. Study staff will review logs during remote check-ins (Weeks 1, 4, 8, and 12). Adherence will be expressed as both total number and percentage of completed sessions (out of 12).
- Safety related to usability will also be captured through the Adverse Event Log, reviewed by the principal investigator at each contact.

## 5.0 Inclusion and Exclusion Criteria/ Study Population

- Potential participants will be found through MUSC Urology clinic visits or electronic health-record (EHR) prescreening. Authorized study staff will identify adults with OAB-wet who are also on stable pharmacotherapy who may meet eligibility criteria.

### *Inclusion Criteria*

- Age  $\geq 18$  years
- Diagnosis of OAB-wet (OAB with urgency urinary incontinence) documented by clinical diagnosis
- Baseline  $\geq 1$  UUI episode/day averaged over a 3-day diary
- Is on a stable pharmacotherapy for OAB (antimuscarinic or  $\beta 3$ -agonist) for  $\geq 4$  weeks, with intent to remain on their medication regimen for the duration of this study
- Has the ability to complete bladder diaries, questionnaires, and attend follow-up visits
- Cognitively intact adult and able to understand study procedures and provide informed consent independently.
  - A study team member at the informed consent conversation will assess cognitive ability and the ability to provide informed consent. Assessment will be based on the participant's ability to understand the study procedures and accurately restate their study roles in their own words. No formal cognitive testing will be performed.

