**Baseline Visit (same day or on a different day):**

- Participants go over the screening results and confirm their enrollment in the study.
- Participants will be instructed that they should remain on stable OAB pharmacotherapy throughout the study.
- They will receive the ZIDA device and get device training based on the ZIDA manufacturer's IFU. They will be instructed to call the study team if, while using the device, they experience any pain, skin irritation, or technical problems.
- They will also be given a 3-day bladder diary and instructions on how to complete it at home over three consecutive days before starting device therapy. This diary records voiding time, urgency, and urgency-urinary-incontinence episodes.
- They will also receive the Device Use Logs, Adverse Event Logs, and Bladder Diaries for the entirety of the study.
- The baseline visit may occur on the same day as the screening visit or may be scheduled for a later date, depending on when all screening procedures are completed and eligibility is confirmed. If all screening assessments are finished during the initial clinic encounter and the participant has enough time to complete the baseline visit, then the baseline visit could be completed. Or, if preferred by the participant, the baseline visit may also be conducted remotely after the screening visit. If this is the case (once eligibility is confirmed) the participant will receive all of the required study materials; the ZIDA device, IFU, conductive gel, and all study logs (Device Use Log, Adverse Event Log, and bladder diaries). Then device training will be conducted either in person or remotely before the participant begins device use. Participants who do not have time to complete all screening and baseline activities in a single visit may return for one additional visit (combined Screening and Baseline visit) to finish any screening procedures and the baseline visit. In all scenarios, the participants will complete all screening procedures, then once they meet eligibility criteria, will receive device training, and receive all study materials before beginning the intervention period.

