**Intervention Period (Weeks 1–12):**

- Participants will self-administer the ZIDA therapy once a week for 30 minutes. They choose a day of the week that works best for them. For each session, the participant will be seated comfortably, they will put conductive gel on the inside of the ZIDA sock, connect the control unit, and turn it on to begin electrical

stimulation. After 30 minutes, the device will automatically turn off. Participants take off the device, clean off any leftover gel. Participants will complete one session every week for 12 weeks (ideally on the same day  $\pm 24$  hours). Reminders may be sent by telephone, secure email, or text message through a HIPAA-compliant system, depending on participant preference. Reminder messages will be brief and only related to the study (e.g., “Please remember to do your session this week”).

- They will be asked to complete a Device Use Log after each session where they will write down the date, duration, and any notes about the session.
- Study staff will conduct remote study check ins at weeks 1, 4 and 8. Participants may choose to do these using a HIPAA-compliant telehealth platform or a phone call. During these check ins, the study team will confirm that patients are using and adhering to the session schedules by reviewing the Device Use Log. During remote visits, adherence will be confirmed either verbally by the participant reading their Device Use Log entries during the call, or through secure REDCap data entry if the participant prefers to complete their weekly log electronically. During these remote visits, the study team will record any adverse events or side effects. Adverse events and device-related complaints are documented on a standardized Adverse Event Log and reviewed by the study team and/or principal investigator. 3 Day Bladder Diaries: Participants will complete additional 3-day bladder diaries at Weeks 4, 8, and 12. Reminders may be sent by telephone, secure email, or text message through a HIPAA-compliant system, depending on participant preference. Reminder messages will only have neutral content that is relevant to the study (e.g., “Please remember to complete your bladder diary this week”). Participants may complete the 3-day bladder diaries on paper or electronically on REDCap given their preference. Paper diaries may instead be reviewed verbally during the telehealth check-in or collected at the final visit.

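### The diary-based entry criterion has no diary scheduled before eligibility is confirmed; if the single pre-treatment diary is used to apply it, regression to the mean enters the primary endpoint as device effect

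*Protocol*

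**What the plan says.** **Entry.** Protocol Section 5.0 (Inclusion Criteria) asks for a *Baseline* value of at least one "UUI episode/day averaged over a 3-day diary".

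**Screening.** The procedures listed for the Screening Visit in Section 10.0 include no diary. Eligibility is confirmed and the patient enrolled once they are done.

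**Baseline visit.** Participants confirm their enrolment and are then "given a 3-day bladder diary and instructions on how to complete it at home over three consecutive days before starting device therapy". The same section says that, in every scenario, patients meet the eligibility criteria before they receive the study materials, and the bladder diaries are among those materials.

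**Later diaries.** "Participants will complete additional 3-day bladder diaries at Weeks 4, 8, and 12".

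**Endpoint and analysis.** This is a "prospective, single-arm, pre-post cohort study" (Section 1.0) in which "Each patient will serve as their own control" (Section 3.0). The primary endpoint is the "mean change in total daily UUI episodes from baseline to week 12" (Section 4.0). Section 11.0 compares pre- and post-device values by paired t-test, or by Wilcoxon signed rank test if necessary. The protocol does not mention regression to the mean.

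**The concern.** There are two linked problems.

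First, a criterion that needs a completed 3-day diary cannot be applied at a point where no diary has been issued. Staff must either use some unspecified source for UUI frequency or apply the threshold after enrolment.

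Second, if they apply it with the only pre-treatment diary, one three-day count both selects the patient and is the value from which week 12 is subtracted. Patients whose count happened to be high that week get in, and those whose count happened to be low do not. The selected mean therefore overstates the true rate, and a repeat diary falls even if the device does nothing. The null hypothesis is zero change and there is no concurrent arm, so the fall would be read as benefit. Section 11.0 says the results will help design a two-arm randomized trial, so an inflated change could mislead that work.

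**Working it through.** **1. The plan's own figure.** Section 11.0 states 85% power with n = 16 and effect size 0.7. For a paired t-test the noncentrality is 0.7 × √16 = 2.8 on 15 df. Power is 84.7% at one-sided 5% and 74.5% at two-sided 5%. With all 20 patients, two-sided 5% gives 84.4%. The protocol states neither alpha nor sidedness, so both are assumptions below. This point does not contest the power figure.

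**2. Which diary can apply the criterion?**

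| Step | Diary available? |
|---|---|
| Screening Visit, eligibility confirmed | None listed |
| Baseline Visit, after eligibility | One 3-day diary issued, completed before device use |
| Weeks 4, 8, 12 | One 3-day diary each, after treatment has begun |

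The baseline-visit diary is the only scheduled one that could carry the threshold, and the word *Baseline* in the criterion points to it. The stated order of events says it comes too late.

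**3. Closed-form check.** If the diary mean is normal and selected above a cut of 1/day, the expected fall on repetition is (1 − ρ) × SD × φ(c)/(1 − Φ(c)), with c = (1 − mean)/SD and ρ the diary reliability. As an assumption, take the prior-study baseline in Section 11.0 (1.2 ± 0.8) as the unselected distribution. Then c = −0.25 and φ/(1 − Φ) = 0.3867/0.5987 = 0.646.

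- ρ = 0.5: 0.5 × 0.8 × 0.646 = 0.26/day
- ρ = 0.7: 0.3 × 0.8 × 0.646 = 0.16/day
- ρ = 0.9: 0.1 × 0.8 × 0.646 = 0.05/day

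**4. Count simulation, no device effect.** Each patient's true daily rate is gamma and 3-day totals are Poisson. Patients with a baseline total of at least 3 are kept, and follow-up is drawn from the same rate. The observed variance is the true-rate variance plus mean/3, so at 1.2 ± 0.8 the reliability is (0.64 − 0.40)/0.64 = 0.375. The test is a paired t-test with n = 16, two-sided 5%.

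| Assumed unselected mean ± SD | Reliability | Selected baseline → follow-up | Spurious fall/day | Fall ÷ SD of change | Rejection | Rejection, separate baseline diary |
|---|---|---|---|---|---|---|
| 1.2 ± 0.8 | 0.38 | 1.65 → 1.37 | 0.28 | 0.31 | 23% | about 5% |
| 1.5 ± 1.0 | 0.50 | 1.91 → 1.71 | 0.21 | 0.20 | 13% | about 5% |
| 2.0 ± 1.3 | 0.61 | 2.34 → 2.21 | 0.135 | 0.11 | 7.6% | about 5% |
| 3.0 ± 2.0 | 0.75 | 3.29 → 3.22 | 0.07 | 0.05 | 5.5% | about 5% |

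Against the decline of 1.2 − 0.3 = 0.9/day cited in Section 11.0, the first row is 0.28/0.9 = 31% and the last is 0.07/0.9 = 8%. At one-sided 5%, rejection is 35% in the first row and 7.5% in the last.

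**5. Sensitivity.** With counts more variable than Poisson (variance up to twice the mean) and means from 1.2 to 3.0/day, the spurious fall ranges from 0.07 to 0.50/day. The chance of a significant apparent benefit ranges from 4% to 35%, against 2.5% in the upper tail of a two-sided 5% test.

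**6. Effect of separating the diaries.** With a second, unselected pre-treatment diary as baseline, the spurious fall is about 0.00/day. Of those enrolled, about 29%, 20%, 12% and 6% (rows in order) would have a baseline below 1/day.

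**The case against.** **The shared diary is inferred.** A reader might take it as established that one diary both selects patients and serves as baseline. The protocol never says so. On the literal order of Section 10.0, the diary is issued after enrolment and selects nobody. If UUI frequency were established some other way, that diary would already be a fresh baseline. This stands, so the bias is conditional. It does not clear the plan: on that reading the diary criterion has no scheduled data source.

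**The size is assumed.** A reader might also infer that the trial has a 23% false-positive rate. The 1.2 ± 0.8 figure is the baseline of another study's enrolled sample, not an unselected clinic distribution for this one. Reliability, alpha and sidedness are not given either. Near 3 episodes/day the bias almost vanishes; with overdispersed counts it is larger than in the main table. This stands.

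**It is a small uncontrolled study anyway.** Placebo response and natural course also enter the estimate, and a second diary does not remove them. The return to about 5% holds only where selection is the sole source of change. The protocol also does not say that the later randomized trial would be sized on this pre-post change. All of this stands. But Section 1.0 states an efficacy aim and a directional hypothesis, and the selection artefact is the one component removable without a control arm.

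**The analysis plan could handle it.** It could discuss the bias, but it cannot supply a diary that was never collected.

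**Conclusion.** The contradiction between the inclusion criterion and the visit sequence is on the face of the protocol and needs reconciling whatever was intended. If the single pre-treatment diary is used to apply the threshold, the primary change is biased toward benefit. That direction is certain whenever diary reliability is below 1.

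The size depends on how close typical UUI lies to the 1/day cut: from 0.28/day with 23% rejection to 0.07/day with 5.5% rejection over the main gamma-Poisson cases. Those figures rest on an assumed population distribution, zero device effect, 16 completers and a two-sided 5% test. The documents support neither treating the shared diary as stated fact nor treating 23% as the trial's actual error rate.

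**What to change.** 1. Schedule a 3-day screening diary after consent and before eligibility is confirmed, used for eligibility only.
2. Use a second 3-day diary, completed before the first device session, as the baseline for all change analyses.
3. Reword the inclusion criterion from *Baseline* to *Screening*, so the threshold is not re-applied to the second diary, and bring the order of events in Section 10.0 into line.
4. Report the screening-to-baseline difference as an estimate of the selection (regression-to-the-mean) artefact. It is not an estimate of 12-week untreated drift. State that placebo response and natural course remain uncontrolled.

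Participation of about 14 weeks with 12 on treatment leaves about 2 weeks, enough for two 3-day diaries (6 days).

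**Cost.** An amendment; three more diary days per participant; loss of the option to complete screening and baseline on the same day; some screen failures on the diary; about 6% to 29% of participants with a baseline below 1/day under the assumptions above; and a smaller apparent effect.

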***Exclusion Criteria***

- Neurologic conditions that affect bladder function, such as multiple sclerosis, spinal cord injury, Parkinson's disease, or other neurogenic bladder conditions.
- Significant pelvic organ prolapses or other pelvic pathology that interferes with bladder emptying, neuromodulation efficacy, or study assessments
- Active urinary tract infection (UTI) or unexplained hematuria at screening
- Clinically significant post-void residual (PVR) volume above threshold (e.g., >100 mL)
- History of, failure of, or current use of neuromodulation therapies, including percutaneous or transcutaneous tibial nerve stimulation (PTNS/TTNS), sacral neuromodulation (InterStim), implantable tibial devices (eCoin)
- Intravesical botulinum toxin injections less than 9 months prior to entry into the study
- Pregnancy or plans to become pregnant during study participation, and women of childbearing age not using contraception. A urine pregnancy test will be performed for women of childbearing potential to confirm non-pregnant status prior to enrollment.
- Contraindications to electrical stimulation (cardiac pacemaker or implanted defibrillator without physician clearance, unhealed wounds near stimulation site, metal implants in the ankle region)
- Significant uncontrolled medical conditions, such as unstable cardiac disease, poorly controlled diabetes mellitus, severe peripheral edema, or severe peripheral neuropathy that may affect lower-limb sensation or response to stimulation in the opinion of the investigator
- Pelvic malignancy of GI, GU or GYN origin, or prior pelvic radiotherapy.
- Current participation in another investigational drug or device trial, or use of an investigational therapy within the last 30 days
- Known hypersensitivity or intolerance to materials used in the ZIDA device (electrode adhesives, conductive gels)

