## **11.0 Data Management**

All data will be limited to clinical and patient-reported outcomes (e.g., bladder diaries, questionnaires, adverse event logs). Collected data will include demographic information

(age, sex), OAB history, current medications, baseline and follow-up diary metrics, and questionnaire scores. Research data will be coded. Identifiable patient information will be stored in a linking document and stored separately from the research data in a password-protected software accessible only to authorized study staff. All study staff will complete CITI training in human subjects research and will be HIPAA compliant. Only de-identified patient data will be removed from MUSC servers. Hard copy documentation (like consent forms and bladder diaries) will be stored in locked cabinets within MUSC Urology research offices. Any data collected electronically (eg. Electronic consents or questionnaires) will be stored in REDCap. Paper responses will be entered into REDCap by study staff, and hard copies stored as source documentation. If any participants complete electronic consent via REDCap's e-consent module, those signed forms will be stored securely within REDCap under MUSC's encrypted server.

- For this single arm pre/post study design, we plan to enroll a total of 20 participants. Since we expect no more than 20% drop-out, this will yield complete data on at least 16 participants. A sample size of  $n=16$  provides 85% power to detect modest changes (effect sizes of 0.7) in study outcomes, including Total Daily Incontinence episodes). Earlier work by Cava & Orlin (2022) suggest that the device may yield an even larger decline in incontinence episodes (i.e. from  $1.2 \pm 0.8$  at baseline down to  $0.3 \pm 0.3$ , at week 12, corresponding to an effect size of 1.4), meaning that we may likely have even greater statistical power. This sample size would also provide sufficient power (>80%) to detect changes in secondary outcomes, including Quality of Life (OAB-Q SF 1W total score). While primary analysis compares baseline to week 12, repeated-measures models will incorporate interim timepoints (weeks 1, 4, 8) descriptively.

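### The entry rule requires stability of OAB drugs only, so improvement from pelvic floor or behavioural therapy begun shortly before baseline would be counted as device effect; the size is unknown, from negligible to about a third of the planned effect.

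*Protocol*

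**What the plan says.** Section 2.0 of the Protocol states: "The conservative treatment options for OAB are lifestyle changes, pelvic floor muscle training, and pharmacotherapy". So the Protocol itself recognises three kinds of conservative treatment.

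Only one of the three is held steady. The Inclusion Criteria in section 5.0 read "Is on a stable pharmacotherapy for OAB (antimuscarinic or" β3-agonist), for at least 4 weeks, "with intent to remain on their medication regimen for the duration of this study". The Baseline Visit text in section 10.0 repeats that scope: "Participants will be instructed that they should remain on stable OAB pharmacotherapy throughout the study".

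The Exclusion Criteria do deal with some other OAB treatments: "History of, failure of, or current use of neuromodulation therapies" and "Intravesical botulinum toxin injections less than 9 months prior to entry into the study", as well as investigational therapy within the last 30 days. They do not mention pelvic floor muscle training, bladder training or lifestyle therapy, whether recent or long-standing.

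The Screening Visit includes a review of medical history and medication. Section 11.0 lists the data to be collected as demographics and "OAB history, current medications, baseline and follow-up diary metrics, and questionnaire scores". Neither place has an item for non-drug OAB therapy.

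On design, section 3.0 says "Each patient will serve as their own control". Section 11.0 compares outcomes before and after device use by a paired t-test or Wilcoxon signed rank test, with no adjustment for other treatment.

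**The concern.** Without a control arm, the change from baseline to week 12 can be read as the effect of adding the device only if the background OAB treatment is steady when baseline is measured. The 4-week drug rule serves that purpose for drugs. Applied exactly as written, the same criteria admit a patient who began pelvic floor training the week before screening, and any improvement she gains from it over the next 12 weeks is added to the device's result.

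A randomised comparison would tend to balance such patients between arms. Here nothing separates the two effects. No named data item identifies these patients, and with about 16 completers a later adjustment is not realistic. Improvement from the other therapy pushes the estimate in one direction, towards the device. Section 11.0 says the results will help to design a definitive two-arm trial, so an inflated estimate could carry over into that trial's sample size.

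**Working it through.** **Is the gap closed anywhere?** The three treatments named in section 2.0, set against the rules:

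| Treatment | Stable at entry required? | Told to keep stable? | Named item collected? |
|---|---|---|---|
| Drugs | Yes, at least 4 weeks | Yes | Yes |
| Pelvic floor muscle training | No | No | No |
| Lifestyle changes | No | No | No |

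The exclusions add neuromodulation, botulinum toxin and investigational therapy, none of which covers the lower two rows. The gap is open.

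**The plan's own power figure.** Section 11.0 gives 85% power for n = 16 and effect size 0.7. For a paired t-test the noncentrality is 0.7 × √16 = 2.8 on 15 degrees of freedom. Power is 84.7% one-sided at 5% and 74.5% two-sided at 5%, so the stated figure reproduces only as a one-sided test. Sidedness is not stated. That is a separate matter and the present point does not depend on it.

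**Scale.** Section 11.0 cites an earlier study of the device with 1.2 ± 0.8 episodes/day at baseline and 0.3 ± 0.3 at week 12, and calls this an effect size of 1.4. If the 1.4 is standardised by the SD of the change, which the Protocol does not say:
- SD of change = (1.2 − 0.3)/1.4 = 0.9/1.4 = 0.643/day.
- Planned effect = 0.7 × 0.643 = 0.45/day.

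**Size of the bias.** The documents give neither the share f of participants with recently begun therapy nor their mean gain g. Both are assumptions: f from 5% to 30%, g of 0.25 or 0.5/day. Spurious mean change = f × g. Rejection is for a device with no effect, n = 16, two-sided 5%, noncentrality = (f × g/0.643) × √16.

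| f | g (/day) | f × g (/day) | Share of 0.45/day | Rejection |
|---|---|---|---|---|
| 5% | 0.25 | 0.0125 | 3% | 5.1% |
| 5% | 0.5 | 0.025 | 6% | 5.2% |
| 10% | 0.25 | 0.025 | 6% | 5.2% |
| 10% | 0.5 | 0.05 | 11% | 6.0% |
| 20% | 0.25 | 0.05 | 11% | 6.0% |
| 20% | 0.5 | 0.10 | 22% | 9.0% |
| 30% | 0.25 | 0.075 | 17% | 7.2% |
| 30% | 0.5 | 0.15 | 33% | 14.1% |

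Worked case, last row: 0.30 × 0.5 = 0.15; 0.15/0.45 = 33%; noncentrality = (0.15/0.643) × 4 = 0.93.

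The calculation treats the bias as a pure shift. Allowing for the extra spread when only some patients gain lowers the upper figures slightly: a simulation of the mixture gave 13.0% in place of 14.1%, and 8.5% in place of 9.0%.

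**The case against.** The best case against the point is about likelihood and size. A reader might infer that many participants will be new starters, since they are recruited in a urology clinic while still leaking on drugs. The documents do not support that. Section 8.0 describes chart prescreening of patients already on stable drugs, and section 2.0 speaks of patients who still leak despite first- and second-line therapy. Both fit equally well with patients who tried pelvic floor or lifestyle therapy long ago. Section 2.0 also says that many patients struggle to keep up lifestyle changes, which argues against a large average gain. A gain of 0.5/day would exceed the whole planned device effect of 0.45/day. These objections stand, and they are why the range starts at negligible.

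It can also be said that this is an omission and not a contradiction. The study question is add-on to stable drug treatment, and the Protocol applies that scope consistently. That is true, but the scope does not alter what the paired comparison measures. The general history review at screening could pick up recent therapy, but nothing requires staff to ask about it or act on it.

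Finally, regression to the mean (entry requires at least 1 episode/day), placebo response and diary effects would remain after any fix. That also stands. The difference is that those need a control arm, whereas this source can be largely removed by an entry rule.

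**Conclusion.** The point holds as a gap in the entry criterion with a known direction and an unknown size. The criteria as written admit patients whose non-drug OAB treatment has just changed, and the design credits any resulting improvement to the device.

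Under the stated assumptions the spurious change runs from about 0.01/day, which hardly moves the error rate, to 0.15/day, a third of the planned effect with 14.1% rejection of a null device. The upper figures should not be taken as an estimate for this trial: the share, the gain and the reading of the 1.4 are all assumptions. Nor should one infer that closing the gap would make the pre-post change a clean device effect; the other limits of a single-arm study stay. The change is still worth making before enrolment, because it is cheap and the analysis cannot recover the information later.

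**What to change.** - **Inclusion Criteria, section 5.0.** Extend the stability criterion so that any pelvic floor muscle training or structured behavioural OAB therapy in use at entry has been unchanged for at least the period already required of the drug therapy, with the same stated intent to continue it as for the medication.
- **Screening Visit, section 10.0.** In the history review already planned, ask about such therapy and its start date, and add both to the data listed in section 11.0.
- **Follow-up.** At the existing check-ins and the final visit, record any such therapy begun after baseline, so that a sensitivity analysis of the primary endpoint can leave those participants out. This is a recording rule only; it should not bar anyone from care.

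The wording is limited to structured therapy because informal lifestyle change has no clear start date. The cost is a short amendment, a question at visits already scheduled, and a wait of some weeks for a few patients. No extra visits or participants are needed. The report should still name regression to the mean and placebo response as limits of the design.
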